- **ATTOC Intervention Adherence Tool (“The Dashboard”):** This web-based tool is used by the study team to track and monitor compliance and progress on the 10 ATTOC steps – on an organizational and on an individual (clinician) level. This adherence measure is used to determine the level of compliance with ATTOC steps so that variability across sites in the implementation of ATTOC can be included in analyses and to guide performance feedback. The dashboard is a visual figure with a numeric indicator using red (no movement), yellow (some progress), and green (completed) colors that enables staff to see progress on key metrics of change. Data are gathered through staff self-report and chart reviews, study measures, and the environmental scan. On an organizational level, examples of metrics include: the selection of a site champion, the use of change and communication plans, the implementation of change plans, additional staff training, the provision of TUD treatment (counseling, referrals, pharmacotherapy), the establishment of a smoke-free campus or progress in establishing smoking restrictions, use of no-smoking signage, inclusion of TUD treatment within SOPs, and provision of TUD treatment brochures. On an individual level, examples of metrics include: the provision of TUD counseling, number of referrals to smoking cessation treatment programs including the Quit-line, and the provision of pharmacotherapy. This dashboard assessment reflects metrics of overall organizational and individual clinician change and is used as a covariate in analyses of study aims and to guide performance feedback to clinic leadership, site champions, and clinicians. We will also include a measure of fidelity to determine whether the ATTOC model was implemented as intended. This measure includes: attendance at on-site training sessions, logging onto the ATTOC program training website, and participation in training teleconference/video calls. The fidelity measure, analogous to a measure of treatment dose, will be expressed as a proportion of the number of training hours received and used as a potential covariate. All personnel participants are expected to interact with the Dashboard and update the metrics. The chosen site champion will be responsible for reviewing the metrics prior to scheduled training sessions and will summarize the findings for the group.

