4.8 Study Endpoints

4.8.1 Primary Study Endpoints

For Aim 1, we will assess adherence to guidelines for treating TUD as done previously [18, 31, 72, 73]. This measure, developed by Delucchi et al. [103], assesses components of the USPHS guideline [20]. Items measure the rate of: asking clients about smoking, advising them to quit, providing assistance with quitting, and arranging visits to track progress. A total adherence score can be calculated [18]. We will supplement this measure with questions about the content, nature, and intensity (in terms of time) of behavioral counseling provided. Clinician adherence will be assessed from the client perspective as well, using the client version of this scale [105], EHR adherence data will be accessed (e.g., documenting smoking status, use of pharmacotherapy), and prescription data (provided and filled) will be accessed by CBH.

For Aim 2, smoking status is assessed using self-reported 7-day point prevalence and CO to verify self-report [66, 106], with abstinence=self-reported abstinence for >7 days prior to the weeks 36 and 52 assessment and a breath CO <8ppm at the time-point [98, 99]. Participants are assumed to be smoking if they self-report to be smoking at the time-point, do not provide self-report or CO data at the time-point, or provide a breath sample at the time-point that is >8ppm [93]. Secondary outcomes will also be assessed (e.g., smoking status at week 12, smoking rate [number of cigarettes/day]).

For Aim 3, client mental health will be measured using several indicators [107]. We will assess the frequency and duration of any illness-related in- client hospitalization (available through the EHR). Clients will complete the Revised Behavior and Symptom Identification Scale (BASIS-R), a 24-item assessment of mental health functioning [108] that yields a total score and subscale scores for: depression, interpersonal relationships, self-harm, emotional lability, psychosis, and substance abuse. The Short-Form Health Survey (SF-12) will assess physical and mental QOL [109, 110].

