Given the necessary complexity of the ATTOC intervention to promote broad, sustainable organizational change, we will use SEM to identify and measure the key elements of ATTOC related to improved outcomes (clinician behavior and client smoking) as has been suggested [18]. We will use the ATTOC Intervention Adherence Tool (i.e., "The Dashboard") to determine each site's compliance with ATTOC's steps (e.g., the selection of a site champion, the preparation of change and communication plans, the implementation of change plans including SOPs, the provision of TUD treatment, the establishment of a smoke-free campus or progress in establishing smoking restrictions). First, we can use SEM with binary predictors (e.g., identified a tobacco champion or not) to determine the relative impact of implementing each ATTOC element so that policy-makers can select a smaller, more manageable number of organizational change elements within ATTOC to implement; this may be especially relevant for disseminating ATTOC to sites which already successfully perform certain aspects of ATTOC already. Second, we can use SEM again to calculate the individual and combined impact of implementing ATTOC elements on outcomes, analogous to determining the "dose" effect of implementing various levels of ATTOC. These analyses will help policy-makers know the likely size of effects from implementing various ATTOC elements and make decisions about what their agency requires.

8 Safety and Adverse Events

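### Exploratory Aim 2: one Dashboard element measures the same thing as the provider-adherence outcome, so that element, and any combined dose containing it, is biased towards a positive association

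*Combined protocol and SAP*

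**What the plan says.** For Exploratory Aim 2, section 7.2.1 sets out to "identify and measure the key elements of ATTOC related to improved outcomes (clinician behavior and client smoking". It takes the predictors from the Dashboard, which is used "to determine each site's compliance with ATTOC's steps". The listed elements include "the implementation of change plans including SOPs, the provision of TUD treatment, the establishment of a smoke-free campus". Structural equation models will first estimate the relative impact of each element, and then "calculate the individual and combined impact of implementing ATTOC elements on outcomes", described as a dose effect. The stated purpose is to help policy-makers choose a smaller set of elements.

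Section 4.7 describes the Dashboard. At site level, provision of treatment is spelled out as counselling, referrals and medication. At clinician level, "On an individual level, examples of metrics include: the provision of TUD counseling, number of referrals to smoking cessation treatment programs" and the provision of medication. On sources: "Data are gathered through staff self-report and chart reviews, study measures, and the environmental scan". Section 6.2.2 says that the Dashboard also carries an index of adherence to the tobacco treatment guidelines.

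Section 4.8.1 defines the Aim 1 outcome as the rate of "asking clients about smoking, advising them to quit, providing assistance with quitting, and arranging visits to track progress", reported by personnel on the S-KAP and supplemented by the client version, EHR data (including medication use) and prescription data. Section 7.2.1 sets the primary time points at Weeks 36 and 52. The schedule in section 6 has Dashboard readings up to Week 36.

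**The concern.** To learn which parts of an intervention drive an outcome, the predictors must be distinct from the outcome. Here one predictor, treatment provided by clinicians, is largely the outcome seen through a second instrument. Clinics whose staff already treat tobacco use more will score higher on both, whether or not naming a champion, writing plans or changing policy did anything.

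Section 7.2.1 does not exclude overlapping items, separate process steps from delivered treatment, or require the Dashboard value to precede the outcome. For provider adherence, the provision element would be favoured in any ranking of elements, and a combined dose would inherit part of that slope. Collecting data from more clinics would not remove the bias.

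**Working it through.** **1. Content, side by side.**

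| | Dashboard predictor | Provider-adherence outcome |
|---|---|---|
| Content | Counselling, referrals, medication (4.7); guideline-adherence index (6.2.2) | Ask, advise, assist, arrange (4.8.1); specific practices such as recommending medication (7.2.1) |
| Source | Staff self-report, charts, study measures, environmental scan (4.7) | Personnel S-KAP; also client S-KAS, EHR and prescription data (4.8.1) |
| Time | Up to Week 36 (section 6 schedule) | Weeks 36 and 52 (7.2.1) |

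Content overlaps throughout, source overlaps in part, and time overlaps for Week 36 only.

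**2. Inputs from the documents.** Section 7.2.1 lists five element groups, one of them provision. The site-level list in 4.7 has about nine metrics, one of them provision. The Dashboard tracks 10 steps. I therefore take 1 overlapping item among 5 to 10. There are 7 ATTOC sites (4.1), 280/14 = 20 personnel per site, and ICCs of 0.05 to 0.15 (7.1).

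**3. The plan's own figure.** Exploratory Aim 2 states none. To confirm the inputs for the shared outcome, I reproduced the Aim 1 detectable difference in 7.1:

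(t.975,12 + t.80,12) × SD × √[2(1 + (m−1)ICC)/(7m)], with SD = 0.87 and m = 20.

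For ICC = 0 this is (2.179 + 0.873) × 0.87 × √(2/140) = 0.317. Over ICC 0, 0.05, 0.10 and 0.15 it gives 0.317, 0.443, 0.540 and 0.623, against the stated 0.32, 0.44, 0.54 and 0.62. The plan's figures reproduce and are not in dispute.

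**4. Expected correlation when no process element works.** Assume K equally weighted, independent, unit-variance items. One correlates r with adherence; the rest do not. The correlation of their sum with adherence is r/√K. The documents give no r; I assume 0.5 to 0.7.

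- K = 10: 0.5/√10 = 0.16; 0.7/√10 = 0.22.
- K = 5: 0.5/√5 = 0.22; 0.7/√5 = 0.31.
- Provision element alone (K = 1): 0.5 to 0.7.

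**5. What this means with 7 sites.** A null simulation (40,000 runs per case) let site adherence vary only through the ICC, and let the provision item reflect true site adherence with reliability 0.5 to 0.8 (assumed). All other items were noise. Site mean adherence was regressed on dose (t-test, 5 df). Items were scored either graded or on/off.

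The graded results can be checked by hand. The reliability of a site mean is λ = 20·ICC/(1 + 19·ICC), which is 1/1.95 = 0.513 at ICC 0.05 and 3/3.85 = 0.779 at ICC 0.15. The provision item's correlation with the site mean is √(reliability × λ): √(0.5 × 0.513) = 0.51 to √(0.8 × 0.779) = 0.79. Dividing by √10 gives 0.16 to 0.25. On/off scoring lowers these somewhat.

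| Dose | Mean correlation | Slope positive | Two-sided rejection at 5% |
|---|---|---|---|
| No provision item | 0.00 | 50% | about 5% |
| 1 of 10 items | 0.13-0.25 | 62-73% | 6-8% |
| 1 of 5 items | 0.18-0.35 | 67-80% | 6-12% |
| Provision element alone | 0.40-0.79 | 86-99% | 15-65% |

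**The case against.** Several points on the other side stand.

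- A reader might infer that the dose is simply the outcome renamed, and that a dose-response must appear. The documents do not support that. The Dashboard is a separate progress tool; the S-KAP is a questionnaire score. They share a construct, and for a combined dose the false-positive rate rises only modestly.
- A reader might reach for larger figures. If three of ten items were provision items (correlated 0.3 to 0.5 with each other), the correlation would be 3r/√(10 + 6ρ): 1.5/√11.8 = 0.44 to 2.1/√13 = 0.58. A clinician-level score made only of the three named metrics would give 3r/√(3 + 6ρ): 1.5/√4.8 = 0.68 to 2.1/√6 = 0.86. Section 7.2.1 works from each site's compliance and lists provision once; it describes neither of these scores.
- Champion, plans and smoke-free progress, estimated separately, are not made spuriously positive. Client smoking is not a listed element, so that outcome is not circular in this way. It would be too broad to say that the whole set of recommendations must be wrong.
- The Week 52 outcome already follows the last Dashboard reading. Charts, the environmental scan, client reports and prescription data also dilute the shared-informant problem.
- Delivering treatment is a genuine ATTOC step (Table 2, step 6), so it belongs in a compliance record. The aim is exploratory and no primary test depends on it.

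None of this removes the shared content. A later outcome visit or a different informant does not make treatment provision a distinct predictor of treatment provision.

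**Conclusion.** The point holds in limited form. For the provider-adherence outcome in Exploratory Aim 2, the provision element (and any guideline-adherence index), taken alone or within a combined dose, has a positive expected association even if no process element works. With 1 overlapping item of 10, the spurious correlation is about 0.16 to 0.22; it is larger for the provision element alone. With 7 ATTOC sites and 1 overlapping item of 5 to 10, the combined dose has a false-positive rate of about 6-12% instead of 5%.

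The sizes rest on assumed item-outcome correlations (0.5 to 0.7) or reliabilities (0.5 to 0.8), equal weights and independent items. The direction needs only that provision and adherence correlate positively. The consequence is a misleading ranking of elements and an inflated dose slope in an exploratory analysis. It is worth correcting because the results are meant to guide which elements clinics adopt.

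**What to change.** In section 7.2.1, specify for Exploratory Aim 2 that, when provider adherence is the outcome:

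- the element set and the combined dose use process items only: champion named, change and communication plans, staff training, SOP or policy change, signage, smoke-free progress;
- treatment-provision and guideline-adherence items are excluded, as is any item drawn from S-KAP, S-KAS or EHR adherence data;
- for the Week 36 outcome, Dashboard values recorded before that visit are used, for example through Week 32.

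Keep the provision items for fidelity monitoring. In the simulation, removing them returns the null correlation to 0.00 and the rejection rate to about 5%.

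The cost is wording only: the process items are already named as Dashboard metrics in 4.7, and the schedule already has a Week 32 reading. The downside is a narrower dose score that no longer covers the full Dashboard.

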4.1 General Design

This cluster-randomized trial will be conducted with 14 Philadelphia CMHCs, 7 randomized to ATTOC and 7 to usual care (UC). Following randomization, study staff will visit sites to recruit clinic personnel and clients over a 4 to 6 week period. Those eligible will complete informed consent and HIPAA forms and a baseline assessment to establish pre-intervention levels on all measures (baseline). After 4-6 weeks, the ATTOC intervention will be implemented over 9 months, from Week 1 to Week 36 (with UC at the control sites). Two mid-intervention assessments (Weeks 12 and 24) will allow for performance feedback (see Outcomes Data) and mediational analyses. Week 36 (end-of-treatment; EOT) and 52 (3-months post-EOT) assessments will allow for evaluation of changes on outcomes between groups over time. All measures will be conducted at the respective CMHC

(or over the phone if necessary) and 7-day point prevalence smoking cessation will be verified using a breath carbon monoxide (CO) monitor (abstinence = < 8ppm; [93]). Figure 1 illustrates the study design.

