4.2 Randomization to Interventional Group

Although randomization and inclusion criteria will increase comparability between arms, sites will be matched by: 1) size (i.e., moderate [15-30 personnel; 110-249 clients] vs. large [>30 personnel; >249 clients]) 2) organizational motivation (e.g., < 30 vs. ≥ 30 on sum of all 12 items from the Organizational Readiness for Implementing Change [ORIC] measure [92]). We will try to enroll >2 sites (1/arm) that do not respond to initial invitations to enroll to include CMHCs with low readiness to implement change. Using the ORIC and outreach to sites with low motivation, we hope to reduce the potential of over-volunteering that can limit generalizability. If a CMHC has multiple locations, all locations will be randomized to the same arm but they will be considered 1 of the 14 randomized sites. Once eligible and interested sites are identified, using the small-sample equivalent to matching on stratification data, they are randomly assigned to UC or ATTOC. Computerized randomization within our Data Management System (DMS) will be provided by [name]. Once randomized, participants (personnel and clients) will be recruited for the trial.

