ATTOC Intervention: ATTOC is implemented in a systematic 3-phase process with 10 steps (Table 2) to guide sites through cultural change and implementation of evidence-based practice. ATTOC is flexible to accommodate the unique needs, barriers, resources, and goals of an agency. Each organization begins at its own starting point based on what it has already accomplished (although, from our experience, most agencies are similarly not systematically addressing TUD at baseline), so the ATTOC intervention starts with diagnosis and proceeds to intervention and evaluation, consistent with ODT. Across the steps within the phases, 7 core strategies are used: 1) Meetings, calls, and video-conferences to prepare for and implement the intervention; 2) On-site consultation and technical assistance, including an Environmental Scan and training; 3) Formation of the agency's Tobacco Champion/Leadership to support culture and practice change, including the use of a "dashboard" assessment to provide performance feedback; 4) Implementation of the agency's change plan to achieve its Client, Staff, and Environmental goals; 5) Formal training/technical assistance in the treatment of TUD at the agency with ongoing monitoring, feedback, and coaching by champions; 6) Sustained consultations, including the use of the dashboard assessment to monitor organizational change and provide performance feedback to clinicians; and 7) Web-based support. The ATTOC intervention will be implemented over 9-months via 10 sessions (as in ongoing ATTOC initiatives): 2 in-person/on-site and 8 by video-conference (or teleconference) (see: <http://www.umassmed.edu/psychiatry/attoc.aspx>). Due to the fact that many community mental health clinics provide fee-for-pay service, the study has budgeted up to \$1,500 per site, depending on the need of the site. This compensation is meant to offset the cost associated with lost time and effort due to study participation on the part of clinic personnel.

6.2.2 Week 1

Usual Care (UC): Clinics will take part in a 1-day training session with [name] and/or [name].

ATTOC Intervention: Week 1 is a 3-day on-site technical assistance and training visit for clinic personnel. Site personnel are not required to attend the entire 3-days and training sessions are divided into blocks so that normal agency functions can occur. This visit involves the following components:

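### Exploratory Aim 2 promises separate effects for each ATTOC element, but seven ATTOC clinics cannot separate about ten site-level elements and barely support five

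*Combined protocol and SAP*

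**What the plan says.** Section 4.1 describes "14 Philadelphia CMHCs, 7 randomized to ATTOC and 7 to usual care (UC"). Section 4.2 says that when an agency has several locations, "all locations will be randomized to the same arm but they will be considered 1 of the 14 randomized sites", so extra locations add no units. Section 6.2.1 states that "ATTOC is implemented in a systematic 3-phase process with 10 steps", and section 4.7 describes the Dashboard as the tool used to "track and monitor compliance and progress on the 10 ATTOC steps".

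For Exploratory Aim 2, section 7.2.1 uses the Dashboard "to determine each site's compliance with ATTOC's steps" and names five groups of steps as examples: champion; change and communication plans; implementation of change plans including SOPs; provision of treatment; smoke-free campus or smoking restrictions. The first analysis is "SEM with binary predictors (e.g., identified a tobacco champion or not"), and its purpose is "to determine the relative impact of implementing each ATTOC element so that policy-makers can select a smaller, more manageable number of organizational change elements". A second SEM is to give individual and combined effects, likened to a dose. The section closes by saying that policy-makers will learn how large the effects of various elements are likely to be and can decide from them.

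Section 7.1 gives power for Aims 1 to 3 and nothing for this aim. No limit on the number of elements, penalisation or rule for combining them is given.

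**The concern.** As section 7.2.1 describes them, the predictors are properties of a site. Information to separate their effects comes from differences between ATTOC clinics in which elements were carried out, and there are seven such clinics. More clients or staff per clinic improve the precision of each clinic's outcome but add no new pattern of elements.

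Several elements may also not vary. Section 6.1.2 asks every ATTOC clinic to name a champion group. The Week 1 visit in section 6.2.2 includes the Environmental Scan and supplies written change and communication plans. An element present at all seven clinics cannot be told apart from the intercept, and the section's own example of a binary predictor, the champion, is one of these.

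What is at stake is the stated use. A ranking from such a model would largely reflect which elements happened to coincide in seven clinics, yet it is offered as a basis for dropping elements when ATTOC is disseminated.

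**Working it through.** **Inputs.** 7 ATTOC and 7 usual-care clinics (section 4.1); 10 steps (sections 4.7, 6.2.1); five example groups (section 7.2.1); SD 0.87, 280 personnel or 20 per clinic, ICC 0 to 0.15 (section 7.1); about 50 clients per clinic (section 5.2). Alpha .05 is taken as two-sided.

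**1. The plan's own figures.** None is given for this aim, so I checked the Aim 1 figures to see which unit drives them. Detectable difference = (t.975 + t.80, 12 df) × 0.87 × √(2[1 + (m − 1)ICC]/(7m)), with 14 − 2 = 12 df.

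| ICC | m = 20 | stated | m = 17 (15% loss) | stated |
|---|---|---|---|---|
| 0 | 0.317 | 0.32 | 0.344 | 0.34 |
| 0.05 | 0.443 | 0.44 | 0.462 | 0.46 |
| 0.10 | 0.540 | 0.54 | 0.555 | 0.56 |
| 0.15 | 0.623 | 0.62 | 0.635 | 0.63 |

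The match is close. A normal-theory version gives smaller values (0.291 at ICC 0, m = 20). The stated power therefore agrees with degrees of freedom counted in clinics.

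**2. Ten elements jointly.** Parameters: 1 + 10 = 11. Seven clinics give at most 7 distinct rows, so the rank is at most 7. Repeating rows for 7 × 20 = 140 personnel or 7 × 50 = 350 clients leaves it at 7. Adding usual-care clinics coded 0 throughout adds one distinct row, so the rank is at most 8. Even if all 14 clinics varied freely, 14 − 11 = 3 df would remain, or 2 with an arm term.

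**3. Fewer elements, ATTOC clinics only.** Six elements: 7 − 7 = 0 df. Five: 7 − 6 = 1 df, with a t critical value of 12.7. In 20,000 simulated designs with five independent elements, the design was full rank in 67%, 42% and 6% of draws at uptake of 50%, 70% and 85%. The uptake rates are assumptions; the rank limit in step 2 does not depend on them.

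**4. One element at a time.** 7 − 2 = 5 df, and t.975 + t.80 = 3.490. Detectable difference in adherence = 3.490 × 0.87 × √([1 + 19 × ICC]/20 × (1/a + 1/b)), where a and b are the clinics with and without the element.

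| ICC | 4 vs 3 | 6 vs 1 |
|---|---|---|
| 0.05 | 0.72 | 1.02 |
| 0.10 | 0.88 | 1.25 |
| 0.15 | 1.02 | 1.44 |

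Section 7.1 quotes a mean change of 0.51 at 3 months for the whole package. A single element would have to do more than that to be detectable, and a one-at-a-time fit still credits it with whatever accompanied it.

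**5. Clustering, conditional.** If an individual-level SEM ignored clustering, the variance of a site-level effect would be understated by 1 + (m − 1)ICC. For 50 clients per clinic this is 1 + 49 × 0.05 = 3.45 to 1 + 49 × 0.15 = 8.35. For 20 personnel it is 1 + 19 × 0.05 = 1.95 to 1 + 19 × 0.15 = 3.85.

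**The case against.** - **No joint ten-predictor model is written down.** A reader might infer that the plan commits to 11 parameters and that nothing can be estimated. The text does not support that: the list of elements is given as examples, the wording is permissive, and small sets or single elements can be fitted. This stands, so the non-identification is conditional on about ten site-level indicators fitted together.
- **Not every element need be constant within a clinic.** Section 4.7 includes clinician-level metrics for counselling, referral and pharmacotherapy, and the section 6 table schedules the Dashboard at ten time points over weeks 1 to 36. These could add information on some elements. Section 7.2.1, however, speaks of each site's compliance and does not plan to use them to separate elements.
- **Usual-care clinics might contribute.** A reader might infer that only ATTOC clinics can have any element. Section 6.2.1 says that agencies differ in what they have already done, and section 7.2 would compare adherence measures across arms. But sections 6.2.3 to 6.2.5 list no Dashboard among usual-care procedures. With five elements coded 0 there and an arm term, 14 − 7 = 7 df remain, of which 7 − 1 = 6 come from usual-care clinics. They inform the between-clinic variance and not which element does what.
- **A dose analysis is already planned.** This stands. Section 2.2 says that the Connecticut work graded agencies by level of implementation, in line with this aim.
- **Clustering.** A reader might infer that clients will be treated as independent. The documents do not say so. Section 7.2 commits generally to mixed models; section 7.2.1 simply does not repeat this for the SEM.

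**Conclusion.** The concern holds in conditional form. Ten site-level indicators fitted jointly are not identified from 7 ATTOC clinics (11 parameters, rank at most 7, or 8 with usual care coded 0). The five listed groups leave 1 residual df within the ATTOC arm. One-at-a-time fits leave 5 df and do not separate elements that occur together. On any of these routes, the promise that policy-makers can choose among elements, or know the size of each effect, goes beyond what the design supports.

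This rests on site-level coding, as section 7.2.1 describes it, and on a multi-location agency counting as one site. The variance factors in step 5 apply only if clustering is ignored, and they are not the main point. A reader might also extend the criticism to the trial's main conclusions. The documents give no ground for that: this is the second exploratory aim, and no primary or secondary aim depends on it.

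**What to change.** In section 7.2.1:

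1. Make the combined dose analysis the single inferential analysis for Exploratory Aim 2. Use one Dashboard composite defined in advance, for example the number of the 10 steps completed at a stated week.
2. Analyse it with clinic as the unit, or with a site random effect and clinic-level degrees of freedom (7 − 2 = 5 within the ATTOC arm). State that the clustering commitment in section 7.2 applies to this aim.
3. Label the result as non-randomised, since the degree of implementation is not allocated, and as imprecise.
4. Report individual elements descriptively only, clinic by clinic.
5. Remove the statements that the results will let policy-makers select elements or know the size of element effects.

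The cost is wording; the Dashboard data are already scheduled. The sponsor gives up the element-ranking claim, and the seven-clinic dose estimate will have a wide interval.
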